No safety data will be collected. Physicians will report adverse event as per usual French process, if appropriate.

5.3.2 **Questionnaires**

Four paper questionnaires will be completed by the patient and one will be completed by the physician. All questionnaires will be returned in the pre-paid reply envelope to the CRO ITEC Services, in charge of the data entry.

5.3.2.1 *Self-assessment patient questionnaires:*

- ▷ SF-36 (McHorney, Ware, et Raczek 1993; Ware et Sherbourne 1992): The SF-36 questionnaire is a generic health status instrument evaluating 8 dimensions through 36 questions: physical functioning, bodily pain, role limitations due to physical health problems, role limitations due to personal or emotional problems, emotional well-being, social functioning, energy/fatigue, and general health perceptions. An additional item provides an indication of perceived change in health (Annexe 15.1).
- ▷ EQ5D-3L (Brooks 1996; EuroQol Group 1990; Rabin et al. 2014): The EQ-5D questionnaire is a generic health status instrument composed of 5 questions and a VAS. The questions explore 5 dimensions: mobility, self-care, usual activities, pain/discomfort and anxiety/depression. Each dimension has 3 levels: no problems, some problems, extreme problems. The visual analogue scale evaluates the perceived health state (Annexe 15.2).
- ▷ FACIT-fatigue (Webster, Cellier, et Yost 2003): FACIT-Fatigue is an instrument that measures overall fatigue and its effects on the general functioning and daily activities through 13 questions. Completion of the questionnaire should be based on a 7-day recall period. Each question has 5 levels: not at all, a little bit, somewhat, quite a bit, very much. Lower scores indicate greater fatigue (Annexe 15.3).
- ▷ Patient global arteritis activity VAS: This VAS measures global arteritis activity on a scale of 100 mm labelled with “no disease activity” (symptom-free and no arteritis symptoms) at the extreme left and with “maximum disease activity” (maximum arteritis disease activity) at the extreme right. The patient will be asked to indicate his/her disease activity by drawing a line on the scale (Annexe 15.4).

5.3.2.2 *Physician questionnaire:*

- ▷ Physician global arteritis activity VAS: This VAS measures global arteritis activity, as described above. The physician will be asked to indicate the patient disease activity by drawing a line on the scale.

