The following endpoints will be described overall and by type of patient (prevalent/incident), by time between signs/symptoms and diagnosis (qualitative variable), and by type of physicians who follows the patient:

- » GCA duration
- » Initial presentation: proportions of patients with cranial GCA, PMR, extracranial GCA, ESR/CRP, general signs
- » Clinical form
 - Proportion of patients with relapse and number of relapse,
 - Proportion of patients with recurrence and number of recurrences,
 - Dose of GCs-dependence
 - Proportion of patients with GCA complications.

Analysis of potential factors associated to relapse will be performed using logistic regression. The associated factors will be defined in the SAP.

- » GCA activity
 - Proportions of each clinical signs/symptoms of GCA activity

- Scores of the patient and physician global arteritis activity VAS (quantitative variable)

The concordance between the scores of the patient and physician global arteritis activity VAS will be evaluated using the kappa coefficient.

The potential factors associated with the increase of the global arteritis activity will be studied.

Description of the health status of GCA patients

» SF-36 questionnaire

The SF-36 is a self-report, 36 item survey measuring health-related quality-of-life. The SF-36 consists of eight scaled scores. A score ranging from 0 (indicating the worse health status) to 100 (indicating the best health status) is assigned for each domain. Scores and missing data of the SF-36 were handled according to the user's manual. The score for each item of SF-36 will be presented (in quantitative) as well as the total score for each domain.

» EQ5D-3L questionnaire

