- GCA activity

- Scores of the physician global arteritis activity VAS will be analysed as quantitative variables and in classes (≤ 50 ; > 50 mm).
- Scores of the patient global arteritis activity VAS will be analysed as quantitative variables and in classes (≤ 50 ; > 50 mm).

The VAS scores of physician and patient will be divided into classes. The same cut-off (≤ 50 ; > 50 mm) for the two scores will be defined by CHUGAI according to their medical relevance.

In this case, the concordance between the scores of the patient and physician global arteritis activity VAS will be evaluated using the kappa K coefficient, which will be interpreted as follows:

- $K < 0.0$: No match
- $0.0 \leq K \leq 0.2$: Poor agreement
- $0.2 < K \leq 0.4$: Fair agreement
- $0.4 < K \leq 0.6$: Moderate agreement
- $0.6 < K \leq 0.8$: Good agreement
- $K > 0.8$: Very good agreement

To evaluate the GCA activity, the score of the physician global arteritis activity VAS will be used. For this score a threshold value = 10 mm was defined and validated by CHUGAI.

Patients with physician's VAS score less than or equal to 10 mm will be considered with "non-active GCA", while patients with physician's VAS score greater than 10 mm will be considered with "active GCA".

In this case, the potential associated factors with the increase of the GCA activity will be studied by logistic regression.

The outcome variable will be GCA (active/ Non-active). First, a univariate analysis will be conducted. All significant factor at the 20% threshold will be selected for a multivariate analysis. A backward elimination procedure will be used with a threshold of 5%.

The associated factors that will be studied are:

- Age (in classes)
- Gender (Male/Female)
- BMI at diagnosis (in classes)
- Smoking status (Smoker/ Former smoker/ never smoker/unknown)
- Prevalent or incident patient,
- Physician who referred the patient,
- Patient considered with late diagnosis by the physician who referred him (Yes/ No)
- Patient with at least one cranial GCA symptom at diagnosis (Yes/No),
- Patients with at least one PMR symptom at diagnosis (Yes/No),
- Patient with at least one extracranial GCA symptom at diagnosis (Yes/No),
- Patient with abnormal value of ESR (ESR>50 mm/h) at diagnosis
- Patient with abnormal value of CRP (CRP> 25 mg/L) at diagnosis (Yes/No),
- Patient with fever at diagnosis (Yes/No),
- Patient with weight loss at diagnosis (Yes/No),

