Table 23 - Efficacy analysis – Multivariate analysis* of the effect of the patients characteristics on the relapse (outcome variable : at least one relapse / no relapse) – Analysis population (N=XX)

Parameter	Complete model		Backward elimination**	
	OR [CI 95%]	pvalue	OR [CI 95%]	pvalue
Variable 1				x.xxxx
XXX (reference)	1.00			
XX	X.XX [X.XX ; X.XX]			
Variable 2				x.xxxx
XXX (reference)	1.00			
XX	X.XX [X.XX ; X.XX]			
.....				

*Multivariate logistic regression on the significant variables at 20% in the univariate analysis
 ** Model after backward elimination at 5%
 The percentages are calculated compared to filled data
 STUDY : CHUGAI-ARTEMIS - Edition date: DDMMYY
 Pgm : EFFICACY\GCA.SAS

Table 24 - Efficacy analysis – GCA activity (VAS score) - Analysis population (N=XX)

Parameter	Statistics	Total (N=XX)
VAS score of the patient	Mean SD Median [Q1 ; Q3] [Min ; Max] Filled, n(%) Missing, n(%)	
VAS score of the patient (in classes) ≤ 50 mm > 50 mm	n(%) n(%) Filled, n(%) Missing, n(%)	
VAS score of the physician	Mean SD Median [Q1 ; Q3] [Min ; Max] Filled, n(%) Missing, n(%)	
VAS score of the physician (in classes) ≤ 50 mm > 50 mm	n(%) n(%) Filled, n(%) Missing, n(%)	

VAS : Visual Analog Scale

The percentages are calculated compared to filled data

STUDY : CHUGAI-ARTEMIS - Edition date: DDMMYY

Pgm : EFFICACY\GCA.SAS

Table 25 - Efficacy analysis - Agreement between VAS of the patient and the physician - Analysis population (N=XX)

Parameter	Statistics	VAS of the physician	
		≤ 50 mm (N=XX)	>50 mm (N=XX)
VAS of the patient ≤ 50 mm > 50 mm	n(%) n(%) Filled, n(%) Missing, n(%)		
Kappa coefficient P-value			

VAS : Visual Analog Scale

The percentages are calculated compared to filled data

STUDY : CHUGAI-ARTEMIS - Edition date: DDMMYY

Pgm : EFFICACY\GCA.SAS

Table 26 - Efficacy analysis – Univariate analysis* of the effect of the patients characteristics on the GCA activity (VAS> 10mm) (outcome variable : GCA active / non-active) – Analysis population (N=XX)

Parameter	OR [CI 95%]	pvalue
Age in classes		x.xxxx
[50 – 70[(reference)	1.00	
≥ 70 years	X.XX [X.XX ; X.XX]	
Gender		...
Male (reference)	...	
Female	...	
BMI in classes (kg/m²)		
Normal (BMI between [18.5-25]) (reference)		
Under weight (BMI <18.5)		
Over weight (BMI between [25.0 ; 30])		
Obesity (BMI ≥ 30)		
Smoking status		
Non-smoker ever (reference)		
Former smoker		
Smoker		
Unknown		

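### Patient–physician agreement on two continuous 100 mm scores rests on one 50 mm kappa with a p-value; no paired estimate with uncertainty is planned

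*SAP*

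**What the plan says.** Protocol 5.3.2.1 describes the patient scale: "This VAS measures global arteritis activity on a scale of 100 mm labelled with" opposite anchors at its two ends. Protocol 5.3.2.2 gives the physician the same scale. Protocol 7.2.3.2 lists both scores as a quantitative variable and then plans: "The concordance between the scores of the patient and physician global arteritis activity VAS will be evaluated using the kappa coefficient". It gives no cut-off.

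SAP 5.5.2 supplies one: "The same cut-off (≤ 50 ; > 50 mm) for the two scores will be defined by CHUGAI according to their medical relevance". No reason for 50 mm follows. On the scores so divided, "the concordance between the scores of the patient and physician global arteritis activity VAS will be evaluated using the kappa K coefficient". The resulting kappa is graded on a verbal scale from no match to very good agreement. Table 25 is the only agreement output. It holds the 2×2 table at 50 mm and the entry "Kappa coefficient P-value".

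Two other items in SAP 5.5.2 matter here. Each score is also summarised on its own ("Scores of the patient global arteritis activity VAS will be analysed as quantitative variables and in classes"), and Table 24 prints the mean, SD, median and quartiles for each rater. For the activity regression, the physician score has a second threshold: "For this score a threshold value = 10 mm was defined and validated by CHUGAI".

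Neither document plans a paired difference, limits of agreement, an intraclass or concordance coefficient, a weighted kappa, or a CI for kappa.

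**The concern.** Cutting two millimetre scores into two classes discards most of what they say about agreement. A pair at 0 and 49 mm agrees perfectly; a pair at 49 and 51 mm disagrees. The kappa that remains depends on how many patients exceed the cut as well as on how closely the raters agree, so its verbal grade is hard to read without the distribution and an interval. The p-value tests kappa against zero, which is not the question: agreement better than chance is expected when both raters score the same patient.

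At stake is the usefulness of one descriptive result. A reader wants to know by how many millimetres patients and physicians differ, in which direction, and how widely this varies between pairs. Table 25 as planned would give a grade instead.

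**Working it through.** The documents state no expected kappa and no VAS distribution, so there is no planned figure to reproduce. What follows is illustration on stated assumptions, apart from the planned size of 300 (Protocol 4.2) and the two cuts, 50 and 10 mm (SAP 5.5.2).

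**Formula.** Kappa = (po − pe)/(1 − pe), where po is the observed and pe the chance proportion of pairs in the same class.

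**1. Dependence on the share above the cut.** Assume bivariate normal latent scores and the same share p above the cut for both raters. Then pe = p² + (1 − p)².

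| Correlation | p | po | pe | kappa | SAP grade |
|---|---|---|---|---|---|
| 0.7 | 50% | 0.747 | 0.500 | 0.49 | moderate |
| 0.7 | 20% | 0.826 | 0.680 | 0.46 | moderate |
| 0.7 | 10% | 0.894 | 0.820 | 0.41 | moderate |
| 0.7 | 5% | 0.939 | 0.905 | 0.36 | fair |
| 0.8 | 50% | 0.795 | 0.500 | 0.59 | moderate |
| 0.8 | 5% | 0.950 | 0.905 | 0.47 | moderate |

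The underlying association is fixed within each correlation, yet kappa drifts down by 0.12 to 0.13. The grade changes only at correlation 0.7, and only when fewer than about 10% of patients exceed the cut.

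**2. Precision.** Simulating 300 pairs at correlation 0.7 with 5% above the cut gives a 95% sampling range for kappa of about 0.11 to 0.58, that is from poor to moderate on the SAP's scale. On average only 15 patients per rater (5% of 300) lie above the cut.

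**3. Size of a gap.** Construct 300 pairs: 270 with physician 5 mm and patient 45 mm, and 30 with physician 60 mm and patient 100 mm. Every patient scores 40 mm higher.
- At 50 mm: po = 1 and pe = 0.9² + 0.1² = 0.82, so kappa = 0.18/0.18 = 1.00, very good.
- At 10 mm: po = 30/300 = 0.10 and pe = 0.1 × 1 + 0.9 × 0 = 0.10, so kappa = 0.
- Lin's coefficient: each rater's variance and the covariance equal 55² × 0.9 × 0.1 = 272.25, so it is 2 × 272.25/(272.25 + 272.25 + 40²) = 544.5/2144.5 = 0.25.

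**4. Direction.** Write the 2×2 counts as both low / patient high only / physician high only / both high.
- 255/30/0/15: po = 270/300 = 0.90, pe = (285 × 255 + 15 × 45)/300² = 0.815, kappa = 0.085/0.185 = 0.459.
- 255/0/30/15: the same kappa, 0.459, with every disagreement reversed.
- 255/15/15/15 (balanced): pe = (270² + 30²)/300² = 0.82, kappa = 0.08/0.18 = 0.444.

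All three are graded moderate.

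**5. What a paired analysis would deliver.** The 95% half-width of the mean difference is 1.96 × SD/√300. For an assumed SD of differences of 10, 20 or 30 mm it is 1.1, 2.3 or 3.4 mm.

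**The case against.** The strongest reply is that the planned outputs show more than the kappa does. Table 24 prints both raters' means, and where the same patients have both scores, the difference of those means is the mean paired difference. The off-diagonal cells of Table 25 show direction across 50 mm. This stands. A reader might infer that a systematic gap would be invisible or would go unreported, and the documents do not support that. What they do leave out is any uncertainty for the difference and any measure of its spread between pairs. The spread cannot be recovered from two separate SDs without the correlation, and since SAP 5.2.1 leaves missing data unreplaced, the two means may rest on different patients.

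A reader might also infer that kappa never reacts to a shift. It often does. With exponential physician scores of mean 12 mm and error SD 8 mm, all assumed, a 20 mm upward shift in patient scores lowers the 50 mm kappa from about 0.72 to about 0.24. The limitation is that kappa alone cannot tell such a shift from random disagreement.

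Third, the 10 mm and 50 mm cuts are not a contradiction. The SAP defines 10 mm for the physician score only, to form the regression outcome. It remains true that physician scores above 10 and up to 50 mm count as active there and share an agreement class with 0 mm here.

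Finally, kappa is specified in the protocol. That is a reason to keep it, not a reason against adding to it. The 50 mm cut itself comes from the SAP.

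**Conclusion.** The point holds as a limited, inexpensive improvement. Agreement between two quantitative scores is assessed formally only by an unweighted kappa at 50 mm, with a p-value and no CI. Under the normal model that kappa moves from 0.49 to 0.36 at correlation 0.7 as the share above the cut falls from 50% to 5%. At 0.8 it moves from 0.59 to 0.47 without changing grade, so it would be too strong to say that the grade merely reflects where the cut falls. The wide sampling range belongs to the 5% scenario, which is an assumption. The 40 mm example is constructed to show what the statistic can miss, not what is likely. None of this touches a primary endpoint: the analysis belongs to one secondary, descriptive objective.

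**What to change.** In SAP 5.5.2 and Table 25:
- Keep the 50 mm kappa and report it with a 95% CI instead of the p-value. This also fits Protocol 7.2.1, which rules out testing and favours confidence intervals. Give the reason for 50 mm.
- Add, for patients with both scores, the number of pairs, the mean difference (patient minus physician) with 95% CI, and Bland–Altman limits of agreement.
- Add an intraclass correlation or Lin concordance coefficient with 95% CI.
- Optionally, add a sensitivity kappa at 10 mm, noting that the SAP defines this threshold for the physician score only.
- State in advance that kappa is not estimable if neither rater scores any patient above 50 mm.

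The cost is a few lines of SAP text and some extra rows in one table, with no new data. The change should be made before database lock.

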5.3.1 Case report form

No information related to patient identity (initials, full date of birth, etc) will be entered in the eCRF.

The following information will be recorded in the eCRF using the data available in the medical file or collected during the visit (as part of the routine patient management):

- » Date of the inclusion visit (the only study visit) and type of visit (outpatient visit, day hospital, in-patient hospitalisation).
- » Patient eligibility criteria.
- » Demographic data:
 - Year of birth, gender,
 - Smoking status (smoker, never smoker),
- » Clinical data:
 - Height, weight (at diagnosis, at the inclusion visit)
 - Medical history:
 - significant past and current comorbidities (e.g. diabetes, high blood pressure, dyslipidaemia, osteoporosis, neuropsychiatric disorders,

depression, insomnia, serious infection disease, parasitic diseases, cancer, stroke, coronary artery disease, ischemic cardiopathy, peripheral artery diseases, adrenal insufficiency, cataract, glaucoma, gastro-intestinal ulcer, digestive perforation, other significant history),

- start and stop date (month, year) of comorbidities
- Comorbidities related to GCs for GCA patients (i.e. which appeared or worsened during GCs treatment according to the investigator judgement).

» GCA patient journey:

- Incident or prevalent patient:
 - Newly diagnosed (i.e. incident) patient will be defined as patient with GCA diagnosis within the last 6 weeks before visit
 - Not newly diagnosed (i.e. prevalent) patients will be defined as patient with GCA diagnosis more than 6 weeks before visit
- Date of initial diagnosis
- Date of GCA signs/symptoms (month and year)
- Physician(s) who referred the patient (General Practitioner, Ophthalmologists, Neurologist, Emergency, Internist, Rheumatologist, Other).

» GCA characteristics:

- Initial presentation at diagnosis and inclusion visit:
 - Cranial (localized headache, scalp tenderness, temporal artery tenderness or decreased pulsation, ischemia-related vision impairment / loss, mouth or jaw pain upon mastication, stroke or transient ischaemic attack (TIA), other)
 - PMR (morning stiffness and/or pain in the shoulder and/or pelvic girdles, inflammatory arthromyalgia, peripheral arthritis, other)
 - Extracranial (large-vessel GCA i.e. thoracic or abdominal aortic aneurysm, myocardial infarction, dilatation, limb claudication, subclavian stenosis, other)
 - ESR/CRP
 - General signs: fever, weight loss (%), health status modification

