7 STATISTICAL METHODS

7.1 Rationale for the number of patients and physicians

7.1.1 *Number of patients required*

Not applicable in a descriptive observational study

7.1.2 *Number of physicians*

Not applicable

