3.5 Patient selection

3.5.1 Patient selection method

Physicians will start patient inclusion only when the study is initiated at their site and when all regulatory authorisations are obtained.

It is expected that 300 patients (prevalent or incident cases) will be recruited in this study. Based on the previous EGB database analysis, there are 2300 incident patients/year in France. Thus, including 300 incident and prevalent patients during the recruitment period, even excluding summer holidays, seems realistic

Each physician will be requested to include consecutively during the inclusion period all the patients meeting the eligibility criteria listed below and accepting to participate in the study.

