5.5 Analyses of secondary objectives

The analysis of the secondary objectives will be also performed on the analysis population.

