- Patient with alteration of the general condition at diagnosis (Yes/No),
- Number of relapses
- Patient has taken at least one immunosuppressants since diagnosis (Yes/No)
- Patient has taken at least one targeted biological therapy since diagnosis (Yes/No)
- Patient has taken at least one other long-term treatment for the medical care of GCA since diagnosis (Yes/No)
- Patient considered with late diagnosis according to calculated time interval between the first medical events related to GCA and diagnosis (Yes/No)
- Cumulative dose of GCs

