*Multivariate logistic regression on the significant variables at 20% in the univariate analysis

** Model after backward stepwise (backward elimination) at 5%

The percentages are calculated compared to filled data

STUDY : CHUGAI-ARTEMIS - Edition date: DDMMYY

Pgm : EFFICACYGCA.SAS

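### In the GCA-activity regression, the unadjusted 20% screen on incident and prevalent patients pooled can drop real associations for the five factors that accumulate after diagnosis

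*SAP*

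**What the plan says.** SAP 5.5.2 (GCA activity) calls a patient active when the physician's VAS at the single visit exceeds 10 mm, and states that "the potential associated factors with the increase of the GCA activity will be studied by logistic regression". The procedure is: "The outcome variable will be GCA (active/ Non-active). First, a univariate analysis will be conducted. All significant factor at the 20% threshold" enters a multivariable model, which backward elimination then reduces at 5%. The footnote to Table 27 confirms the gate: "Multivariate logistic regression on the significant variables at 20% in the univariate analysis".

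The population is not split. SAP 5.5 states: "The analysis of the secondary objectives will be also performed on the analysis population". SAP 3.5.1 describes the sample: "It is expected that 300 patients (prevalent or incident cases) will be recruited in this study". Protocol 5.3.1 separates the two types: "Newly diagnosed (i.e. incident) patient will be defined as patient with GCA diagnosis within the last 6 weeks before visit".

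The SAP lists 21 candidates. Patient type is one of them and has a row in Table 26, but it is screened and can be eliminated like any other. Time since diagnosis is not a candidate, although item 3 of the SAP's statistical appendix derives it. Five candidates build up after diagnosis: "Number of relapses", the three flags for immunosuppressant, biologic and other long-term treatment since diagnosis, and cumulative glucocorticoid dose. The remaining 15 (21 − 5 − 1) are demographic, referral or at-diagnosis items.

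**The concern.** A patient at most 6 weeks from diagnosis has had little time to relapse, receive an adjunct drug or build up steroid dose. If such patients are also more often rated active, because the disease has only just presented, patient type confounds all five accumulating factors in the same direction. Among prevalent patients a factor may go with more activity. Pooling adds a block of active patients with a value near zero, which cancels part of that association.

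The screen is where this does damage. Patient type may adjust the factors that reach Table 27, but a factor lost at the screen is never adjusted. The analysis could therefore miss, for example, relapse history. In the other direction, a factor with no effect can show a crude odds ratio below 1 with a small p-value in Table 26, which a reader may take as a finding about steroid dose or adjunct treatment.

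**Working it through.** **Inputs from the documents.** 300 patients (SAP 3.5.1); screen at 20% and retention at 5% (SAP 5.5.2); 6-week cut-off (Protocol 5.3.1). There is no planned power or effect size to reproduce: Protocol 7.1 says of patient numbers "Not applicable in a descriptive observational study".

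**Assumed, because the documents do not give them.** Incident share, activity rate by patient type, and distribution of each factor by patient type. The models below contain only the factor under study and patient type.

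**Step 1: pooled odds ratio, binary accumulating factor.** Take 20% incident. The factor is present in 5% of incident and 30% of prevalent patients. Without it, 80% of incident and 35% of prevalent patients are active. The true odds ratio within each type is 2.

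- Share with the factor: 0.2 × 0.05 + 0.8 × 0.30 = 0.25.
- Active without it: (0.19 × 0.80 + 0.56 × 0.35) / 0.75 = 0.464.
- With it, the odds double: incident 4 → 8, so 0.889; prevalent 0.538 → 1.077, so 0.519. Active: (0.01 × 0.889 + 0.24 × 0.519) / 0.25 = 0.533.
- Pooled odds ratio: (0.533/0.467) / (0.464/0.536) = 1.32, not 2.

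If the factor has no effect, the rate with it is (0.01 × 0.80 + 0.24 × 0.35) / 0.25 = 0.368, and the pooled odds ratio is (0.368/0.632) / (0.464/0.536) = 0.67, not 1.

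**Step 2: chance of passing the screen (true odds ratio 2).** With 75 and 225 patients, SE = √(0.533 × 0.467/75 + 0.464 × 0.536/225) = 0.0665. The difference is 0.069, so z = 1.04 and the pass probability is Φ(1.04 − 1.28) ≈ 0.41. Simulation of the SAP rule also gives 41%: the real factor is dropped about 59% of the time.

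**Step 3: final model.** The factor ends significant at 5% in 40% of runs under the SAP rule, against 69% with patient type kept in. With 10-40% incident and 60-90% of them active against 30-35% of prevalent patients, the ranges are 5-70% and 57-73%. With 5% incident the figures are 75% and 77%.

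**Step 4: relapse count.** Simulated with n = 300, no relapses in incident and Poisson(0.8) in prevalent patients, about 35% of prevalent patients active, and a true odds ratio of 1.5 per relapse. Ranges are across repeated simulations.

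| Incident share | Incident active | Detected, SAP rule | Detected, patient type kept in |
|---|---|---|---|
| 20% | 85% | 10-11% | 76-77% |
| 20% | 70% | 24-26% | 76% |
| 20% | 60% | 42-45% | 75-77% |
| 10% | 85% | 46-47% | 77-82% |
| 5% | 85% | 74-75% | 83-84% |
| equal activity | 35% | 71-73% | 77% |

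**Step 5: no true effect.** In the Step 1 setting the factor is crudely protective at p < 0.05 in 29% of runs (nominal 2.5%; range 5-88%). In the final model this falls to 2.5% (range about 2-3%), because patient type passes its own screen in 92-100% of these runs and then adjusts the factor.

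**Step 6: at-diagnosis factor, 40% in both types.** With no effect it passes the screen in 21% of runs and ends significant in 5%. With a true odds ratio of 2 it ends significant in 78%, whether or not patient type is forced in.

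**The case against.** The strongest reply is that patient type is already a candidate, so the plan adjusts for it whenever it matters, and that crude odds ratios followed by adjusted ones are ordinary reporting in a table titled as univariate. Much of this stands. A reader might infer that the final model will report false protective factors; Step 5 shows that it does so only at about the nominal rate. A reader might also infer that the whole screen mainly compares incident with prevalent patients; Step 6 shows that for the 15 factors with no built-in link to patient type it works nearly as intended. The reply does not reach a factor already dropped at the screen.

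The size is also open to challenge. The 20%/85% setting lies almost at exact cancellation (pooled odds ratio 0.98) and should not be read as the expected loss. The activity gap itself is not secure: eligible patients are starting or already under treatment, and Protocol section 1 describes rapid improvement on high-dose glucocorticoids. This stands, and it is why the result is given as a range.

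Forcing patient type in is not a full cure. If the log-odds of activity fall by 0.3-0.5 per year since diagnosis (an assumption), a cumulative dose with no effect, adjusted only for patient type, was still protective-looking in 47-87% of simulated studies. Nor is a prevalent-only fit equivalent: it changes the population and reduces n.

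Finally, this is an exploratory secondary analysis, and SAP 5.5.2 plans to describe activity by patient type. That limits the stakes but does not change the screen.

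**Conclusion.** The concern holds for the screening step and the five accumulating factors. Pooling without adjustment can remove a real positive association before the multivariable model is fitted. The same pooling can make crude odds ratios in Table 26 look protective, but not those in Table 27 beyond the nominal rate.

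The loss ranges from severe (about 11% against 76% detection) to modest (about 74% against 83%), and there is no distortion if incident and prevalent patients are equally often active. Which case applies depends on the incident share and the activity gap, and neither is in the documents. The change is still worth making, because the direction of the confounding can be foreseen and the adjusting variable is already collected.

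One related mismatch: number of relapses is in the SAP 5.5.2 list but has no row in Table 26.

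**What to change.** In SAP 5.5.2 and Tables 26-27:

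- Force type of patient (incident/prevalent) into every screening model, and keep it in the multivariable model whatever its p-value.
- For the five accumulating factors, preferably also include time since diagnosis, because the 6-week split leaves confounding by disease duration.
- Label any univariate odds ratios kept in Table 26 as unadjusted, and add the missing row for number of relapses.
- Offer a prevalent-only fit as a sensitivity analysis, not as a substitute.
- Describe the results as factors associated with active disease at the inclusion visit.

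The cost is SAP wording and one or two covariates already collected or derived. Where activity does not differ by patient type, forcing it in changed detection little: 77% against 71-73% for the relapse count, and 64% against 68% for a binary factor with odds ratio 2 and 40% incident. Time since diagnosis is likely to be correlated with cumulative dose, so the interval for dose may widen.
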